### 10.2. Total number of subjects to be enrolled across all participating sites:

N/A

### 10.3. Number of screened subjects versus the actual number enrolled in the research:

**Aim 1:** We estimate that we will need to screen 400 clinicians to enroll 200 eligible participants and 400 parent-adolescent dyads to enroll 200 eligible participant dyads.

**Aim 2:** We estimate that we will need to screen 80 dyads and/or triads in order to enroll 40 dyad and/or triad participants.

**Aim 3:** We estimate that we will need to screen 40 clinicians to enroll 20 participants.

**Aims 4a and 4b:** We estimate that we will need to screen 100 dyads or triads to enroll 40 eligible participant dyads or triads (20 dyads or triads per phase). We estimate that we will need to screen 25 healthcare providers to enroll up to 20 (Aim 4b only).

### 10.4. Power analysis:

**Aim 1:** This data is primarily being assessed for qualitative responses; therefore, no power analyses are being assessed.

**Aims 2 & 3:** This data is primarily qualitative, and thus a power calculation is not appropriate.

**Aim 4a and b:** We anticipate enrolling 20 families per study phase; allowing for 15% attrition an estimated 17 per phase would complete the study. Conservatively estimating 15 families per phase, we will have  $\geq 80\%$  power to detect a difference in decisional regret (range: 0 to 100 points) as small as 7.1, 3.0 and 1.2 points, for SD = 12, 5, and 2, respectively. These estimates assume an alpha of 0.05 and SD ranging from 1-12. The data from the healthcare provider survey is primarily qualitative, and thus a power calculation is not appropriate.

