**Developing a Tool to Support Shared Decision-Making Post-Concussion  
Between Adolescents, Parents and Clinicians**

**NCT Number:** NCT04777864

**Document Date:** 03/17/2022

*Due to the smaller sample recruited we simplified our analytic plan to focus on between-condition comparisons for the primary decision-related outcomes and no subgroup comparisons.*

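### Section 10.4 claims at least 80% power for Aim 4, but 15 families per phase give about 35% for the differences it states

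*Combined protocol and SAP*

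**What the plan says.** Section 10.4 (Power analysis, Aim 4a and b) plans 20 families per phase, "allowing for 15% attrition an estimated 17 per phase would complete the study". It then steps down once more, "Conservatively estimating 15 families per phase", and claims that the study can, with power of at least 80%, "detect a difference in decisional regret (range: 0 to 100 points) as small as 7.1, 3.0 and 1.2 points". The three differences belong, in that order, to assumed SDs of 12, 5 and 2. Alpha is 0.05. The section names no test, sidedness, covariate, correlation or repeated-measures assumption.

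Section 5.1 describes Aim 4 as a consecutive cohort design, so the two phases contain different families. Section 14.1 compares the control and intervention groups with parent and child measures modelled in parallel, and allows for non-independence within a family.

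The cover page adds: "Due to the smaller sample recruited we simplified our analytic plan". It gives no number recruited, and the text of section 10.4 remains tied to 15 per phase.

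**The concern.** Each stated difference is about 0.6 of its SD. A two-group comparison with 15 per group normally needs an effect slightly above one SD for 80% power, so the stated differences look far too small for the sample.

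This paragraph is the only quantitative justification for the Aim 4 comparison, which section 1.1 describes as assessing efficacy. A reader who accepts it could take a non-significant result as evidence against a 7-point effect. If the SD is near 12, the study would in fact miss such an effect about two times in three. The cover note keeps the between-condition comparison of the primary decision-related outcomes, so the power statement bears directly on the analysis that remains.

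**Working it through.** **Inputs (section 10.4).** n = 15 per phase; alpha 0.05; power at least 80%; differences 7.1, 3.0 and 1.2 points; SD 12, 5 and 2. The attrition step is sound: 20 × 0.85 = 17. Two independent groups are taken from sections 5.1 and 14.1. A two-sided test is assumed first because sidedness is not given.

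**Step 1. Standardised differences.** d = difference / SD: 7.1/12 = 0.592; 3.0/5 = 0.600; 1.2/2 = 0.600.

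**Step 2. Trying to reproduce the 80%.** Two-sample t test, noncentrality = d × √(n/2), 28 degrees of freedom:

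- d = 0.592: 0.592 × √7.5 = 1.62, power 34.7%
- d = 0.600: 0.600 × √7.5 = 1.64, power 35.5%

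The normal approximation gives 36.7% and 37.6%. The stated figure is not reproduced.

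**Step 3. What 15 per phase can detect.** Solving the same t test for 80% power gives d = 1.060:

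| Families per phase | d for 80% power | SD 12 | SD 5 | SD 2 | Power for the stated differences |
|---|---|---|---|---|---|
| 15 | 1.060 | 12.7 | 5.3 | 2.1 | 35% |
| 17 | 0.991 | 11.9 | 5.0 | 2.0 | 39–40% |
| 20 | 0.909 | 10.9 | 4.5 | 1.8 | 45–46% |
| 45 | 0.597 | 7.2 | 3.0 | 1.2 | 79–80% |
| Stated for 15 | 0.59–0.60 | 7.1 | 3.0 | 1.2 | at least 80% |

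The detectable differences at 15 per phase are about 1.8 times those stated (12.7/7.1 = 1.79; 5.3/3.0 = 1.77). All three pairs fail by nearly the same factor, and all three match about 45 per group. With the normal approximation, 45 per group gives 7.09, 2.95 and 1.18. A slip in a single number would not do this.

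**Step 4. Other readings at 15 families per phase.**

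| Reading | Power for the stated differences |
|---|---|
| One-sided alpha 0.05 | 47–48% (80% power needs 0.93 SD, or 11.2 points at SD 12) |
| Parent and adolescent as 30 independent people per phase | 62–63% two-sided (80% power needs 0.74 SD, or 8.8 points at SD 12); 73–74% one-sided |
| Mean of parent and adolescent scores, two-sided | 60–61% at within-family correlation 0; 38–39% at 0.8 |
| Paired or one-sample test, two-sided (not this design) | 57–58% |

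With covariate adjustment, 80% two-sided power would need a covariate correlated about 0.82 to 0.83 with the outcome. The plan gives none.

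**Step 5. Precision.** The half-width of a 95% interval for the difference at 15 per phase and SD 12 is 2.048 × 12 × √(2/15), or about 9.0 points. That is wider than the 7.1-point difference itself.

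**The case against.** The strongest counter-argument is that 45 is exactly 15 × 3, and the documents contain possible threes: section 10.3 mentions triads, and section 5.4 plans surveys at a minimum of three time points. The authors may have counted three observations per family. That could explain the figures, but it does not validate them. Section 10.4 speaks of families and mentions no such unit, section 10.1 plans dyads, and section 14.1 expects family members to be correlated. Averaging three measures over 15 families gives 77–78% two-sided power at zero correlation, 70–71% at 0.1 and 48–49% at 0.5. Adding a one-sided test would pass 80% at correlations up to about 0.1, but the plan states neither condition. Where 45 came from remains an inference.

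It is also fair that 35% is conditional on a simple two-sided comparison of one measure, whereas section 14.1 plans structural equation modelling. The two-in-three miss rate for 7.1 points likewise applies at SD 12; with a smaller SD the same 7.1 points would be easier to detect. Both conditions should be stated.

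Finally, section 1.1 calls Aim 4b a pilot and section 1.2 says that no hypotheses are explicitly tested. Low power may be acceptable in a pilot. Claiming at least 80% when the stated inputs do not give it is still an error, and the cover note does not correct it.

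**Conclusion.** The power statement is wrong as written. With two independent groups of 15 families and two-sided alpha 0.05, power for 7.1, 3.0 and 1.2 points at SD 12, 5 and 2 is about 35% (t test) or 37–38% (normal approximation). The stated differences would need about 44 to 46 families per phase, roughly three times the number assumed.

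The exact figure depends on the test, sidedness and unit of analysis, which section 10.4 omits. That power falls short of 80% does not depend on choosing between a one-sided and a two-sided test, or between the family and two independent people as the unit. Only favourable assumptions that the plan does not state, such as a very strong covariate or three nearly uncorrelated measures per family, would bring power to about 80%.

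**What to change.** Restate the Aim 4 paragraph of section 10.4, for example: with 15 families per phase and two-sided alpha 0.05, a two-sample comparison has 80% power to detect differences of 12.7, 5.3 and 2.1 points for SD 12, 5 and 2; power for 7.1, 3.0 and 1.2 points is about 35%. If the authors intended another test, sidedness or unit of analysis, they should state it with the assumed within-family correlation and recompute.

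State that Aim 4 estimates the between-condition difference with a 95% confidence interval (half-width about 9.0 points at SD 12 with 15 per phase), and that a non-significant result is not evidence of no effect. This second part is reporting advice rather than an arithmetic correction, but it suits a pilot. Give the number of families recruited and repeat the calculation for it, since the cover note says the sample was smaller.

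The cost is wording only. The figures become less favourable, and no extra families or procedures are needed.

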## 11. Withdrawal of Subjects

**11.1.** Anticipated circumstances under which subjects will be withdrawn from the research without their consent:

We do not anticipate circumstances under which participants will be withdrawn from the research without their consent.

**11.2.** Procedures for orderly termination:

N/A

**11.3.** Procedures that will be followed when subjects withdraw from the research, including partial withdrawal from procedures with continued data collection and withdrawal from data/biospecimen banking:

Participants may withdraw from the study at any time by notifying study personnel. Once a participant expresses their desire to withdraw, the researcher will terminate data collection. The study team will review, on a case-by-case basis, whether partial data collected will be used in the analysis.

## 12. Risks to Subjects

**12.1.** Reasonably foreseeable risks to subjects (include each study population, each arm, and optional procedures):

This study involves no more than minimal risk to participants. Potential risks include the risk of loss of confidentiality and the following:

**Aim 1:** Testing burden – participants may experience inconvenience associated with answering survey questions.

**Aims 2 & 3:** Loss of confidentiality – participants may provide identifiable information about themselves, and in the case of parents, their adolescent.

**Aims 4a and 4b:** Testing burden- participants may experience inconvenience associated with answering survey questions; Loss of confidentiality—participants may provide identifiable information about themselves, and in the case of parents, their adolescent

**12.2.** Procedures with unforeseeable risks:

N/A – there are no procedures that pose unforeseeable risks.

**12.3.** Procedures with risks to an embryo or fetus should the subject be or become pregnant:

N/A

**12.4.** Risks to others who are not subjects:

N/A

**12.5.** Procedures performed to lessen the probability or magnitude of risks:

All data will be kept in secure and locked locations. Additionally, all participants will be given the option of speaking to a research study team member at any time, to ask questions or express concerns over research participation. See section 15.1 for additional details on steps that will be taken to mitigate risks to confidentiality.

## 13. Potential Benefits to Subjects

**13.1.** Potential benefits that individual subjects may experience from taking part in the research:

There is no anticipated benefit of participating in this study.

#### 14. Data Analysis/Management

##### 14.1. Data analysis plan, including statistical procedures:

**Aim 1:** Survey responses will be reviewed with a focus on the psychometric properties of items and scales (e.g., how are items distributed), as well as evaluate what answers are correlated. We will compare responses across key characteristics (e.g., clinician characteristics, beliefs) to determine what key beliefs and feedback are across all clinicians, parents, and adolescents.

**Aim 2 & 3:** Thematic analysis will be used to systematically code transcripts and identify emergent themes. Qualitative data will be digitally recorded and transcribed verbatim and coded for relevant themes using a thematic analysis approach. Coded segments may be entered into a qualitative coding software (e.g., Dedoose) to facilitate analysis or will be analyzed by quantified elements. Data will continue to be conducted until emergent results iteratively inform and clarify the final version of the decision aids.

**Aim 4a and b:** We will compare socio-demographic (e.g. age, sex, health literacy) and clinical characteristics (e.g. concussion history and severity at baseline) between the control and intervention groups. Differences in primary decision process and quality outcomes will be compared between treatment and control conditions using Structural Equation Modeling, where parent and child measures will be examined in parallel. Family level non-independence will be modeled by residual covariances between parent(s) and child measures. Outcomes will be pooled across the retirement recommended and equipoise conditions as decision process and quality measures are equally relevant in both conditions. Secondary analyses related to health behaviors (contact sport participation and physical activity) and health status outcomes at Time 3 will be compared between treatment and control conditions using logistic regression.

**Dyadic and triadic analyses.** Dyadic/triadic concordance will first be described using contingency tables. Next, actor-partner interdependence models will be used to assess the effects of each family member's decision process measures on their own decision quality measures and the rest of the family's decision quality measures ("partner" effects). Healthcare provider survey responses will be reviewed and compared to determine key beliefs and feedback across all healthcare providers.

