**Aim 3 (continued):** Second, this aim will conduct usability testing with clinicians (including pediatricians and family medicine providers) for a clinician-specific decision aid. The findings from Aim 1 and Aim 2 will help inform the creation of a clinician-specific decision aid. Findings from this aim will be used directly in Aim 4.

**Aim 4:** This aim has two cohorts:

Aim 4a: Cohort 1 will evaluate how shared decision making currently occurs in a clinical appointment. This data will then be used to compare need and impact of the intervention group in Aim 4b.

Aim 4b: Cohort 2 includes a pilot random control trial (RCT) of all three decision aids (i.e., parent, adolescent, clinician) to assess intervention efficacy of all decision aids in aiding family shared decision making in returning to sport post-sport related concussion.

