### 1.2. Hypotheses to be tested:

This research is qualitative; therefore, we do not have any hypotheses to explicitly test.

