**Many U.S. families are concerned about concussion and seek counsel from clinicians about sport participation post-injury.** Yet clinicians struggle with how to discuss with families whether or not child patients should return to contact sport post-concussion. In part this is because the evidence supporting each option is not definitive. It is also due to the fact that this decision is highly individualized. Influential factors in this decision include clinical variability (e.g., injury severity, recovery trajectory, type of functional impairment post-injury, the interval between prior injuries, the age at which injuries occurred, and premorbid health conditions), and different family tolerance for the uncertain risk of harm associated with sustaining an additional concussion relative to what they see as the benefits of returning to sport and the risks and benefits of substitute activities. Given this context, a recent report by the Institute of Medicine indicates a need for effective communication and dissemination strategies to facilitate decision-making post-concussion among athletes, parents and other stakeholders.

**Shared decision-making is appropriate for return to sport decisions after concussions that do not result in medical disqualification.** Not all options have to be equivalent in terms of their medical burden for shared decision making (SDM) to be appropriate, if all meet current standards of care. There are two main situations in which our formative interviews with clinicians indicate SDM would be appropriate: (1) the clinician believes that medical harms of returning to contact/collision sport outweigh benefits, but the burden does not reach the threshold of mandatory medical disqualification (“retirement recommended”), and (2) the clinician believes there is medical equipoise between the costs and benefits of returning to contact/collision sport but the family is concerned (“no recommendation”). In the “retirement recommended” condition, the clinician would share a recommended course of action (e.g., ceasing contact/collision sport) and attempt to help the family—adolescent and parents—embrace the values and preferences that align with this recommendation. In the “no recommendation” condition, SDM would

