appropriately take a patient-led form, with the clinician in a facilitative role. While decision-making post-concussion with minors will necessarily also involve parents, explicit efforts to elevate the voice of adolescents, particularly when there is medical equipoise in the decision, is developmentally appropriate and supports growth in their efficacy in making healthcare related decisions.

**A decision aid can help facilitate higher quality shared decision-making post-concussion.** High quality decisions are facilitated by a decisional process where: all parties involved recognize that a decision has to be made, feel informed about the risks and benefits of key options, and are clear on what matters most to them. At present, these criteria are inconsistently met post-concussion. Many parents and adolescents are inadequately informed about the short- and long-term risks of concussion, with this deficit magnified among lower socioeconomic status families. Discussions about possible contact/collision sport retirement tend to occur when the clinician believes cessation would be medically beneficial, often around 4 concussions or after concussions with prolonged symptoms. However, we have found that most parents of youth football players would prefer this conversation to be initiated earlier after 1 or 2 concussions ([name] et al., under review). We have also found that timing of this conversation is influenced by the clinician's subjective assessment of the athlete's on field and academic potential. Use of a decision aid post-concussion could help clinicians have a better balanced discussion on the timing and nature of post-concussion communication about sport retirement, ensuring that all families are informed about relevant risks and benefits of different sport options.

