**3.2. Primary or secondary safety endpoints:**

There are no primary or secondary safety endpoints for this study.

**4. Drugs, Devices and Biologics****4.1.** Manufacturer and name of all drugs, devices and biologics:

N/A

**4.2.** Description and purpose of all drugs, devices and biologics:

N/A

**4.3.** Regulatory status of all drugs, devices and biologics:

N/A

**4.3.1.** Drugs or Biologics:

IND Exempt. Explain: [Click here to enter text.](#)  
 IND.

**4.3.2.** Devices:

IDE Exempt. Explain: [Click here to enter text.](#)  
 Abbreviated IDE / Non-Significant Risk. Explain: [Click here to enter text.](#)  
 IDE / Significant Risk.

**4.4.** Plans to store, handle, and administer any study drugs, devices and biologics so they will be used only on subjects and be used only by authorized investigators:

N/A

**5. Procedures Involved****5.1.** Study design:

This study involves the following procedures:

**Aim 1:** Survey**Aim 2:** Interviewing (i.e. qualitative) and Usability Testing**Aim 3:** Interviewing (i.e., cognitive, qualitative) and Usability Testing**Aim 4a and 4b:** Consecutive cohort design (families). Healthcare providers will also complete a one-time survey.**5.2.** Research procedures:

**Aim 1: Clinicians:** This aim will survey clinicians about their current knowledge and belief of concussion research, their experiences with discussing return to sport post-concussion with families, and their opinions for best practices and needs for an effective shared decision-making aid with families on this topic. Participants will receive a link to an online survey, hosted on a survey-hosted site (e.g., REDCap). Before beginning the survey, participants will read an information sheet about the study and then proceed to the survey, which will ask them questions relating to the topics described above. After completing the survey, participants will be exited from the survey and data collection will end for this aim. Survey questions can be found in the attachment section on Click.

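### Aim 4 compares two consecutive, non-randomised cohorts with no named baseline covariate, while Aim 4b is described as a pilot RCT

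*Combined protocol and SAP*

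**What the plan says.** Section 1.1 says of Aim 4b: "Cohort 2 includes a pilot random control trial (RCT) of all three decision aids". Section 5.1 describes Aims 4a and 4b together as "Consecutive cohort design (families"). Under section 5.2, families in the first cohort receive usual provider communication and families in the second receive the decision aids. Section 5.4 identifies the intervention group with 4b alone. Under section 19.1, Aim 4a recruits from the start of the study, and Aim 4b recruits once the aids have been built from Aims 2 and 3.

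Section 14.1 compares socio-demographic characteristics (age, sex and health literacy are the examples) and "clinical characteristics (e.g. concussion history and severity at baseline) between the control and intervention groups". It then says: "Differences in primary decision process and quality outcomes will be compared between treatment and control conditions using Structural Equation Modeling". The only further terms named are residual covariances between parent and child measures. The title-page note says that, because fewer families were recruited, "we simplified our analytic plan to focus on between-condition comparisons for the primary decision-related outcomes"; it mentions no adjustment. Section 1.2 says of the research as a whole: "we do not have any hypotheses to explicitly test".

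**The concern.** Condition here is the same thing as calendar period. Every 4a family is a control and every 4b family is treated, so the design does nothing to balance the two groups. The residual covariances deal with parent and child answering for the same family; they do not deal with confounding. Comparing baseline characteristics describes an imbalance but leaves the effect estimate unchanged.

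The background gives reasons to expect that case mix could matter. Section 2.1 says: "Influential factors in this decision include clinical variability (e.g., injury severity, recovery trajectory". It also says that clinicians tend to raise retirement "often around 4 concussions or after concussions with prolonged symptoms", and that families of lower socioeconomic status are less well informed. If the cohorts differ on such factors, and the factors relate to decision quality or regret, the contrast mixes that difference with the effect of the aids. The randomised-trial wording would lead a reader to credit the comparison with a protection that it lacks.

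**Working it through.** **Design, section against section.** Section 5.1 (consecutive cohorts), section 5.2 (usual communication first, aids second) and section 5.4 (intervention group is 4b only) agree with each other. Section 1.1 does not fit them: with no control families inside 4b, there is nothing within Cohort 2 to randomise between. The recruitment windows need not cover the same months. Aim 3 recruits after Aim 1 is complete (section 19.1), and each is planned at 3 months, up to 5 (section 8.2). Aim 4b would therefore start about 3 + 3 = 6 to 5 + 5 = 10 months after Aim 4a, which itself is planned to recruit for 6 months (possibly 12).

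**The plan's own figure.** Section 10.4 states at least 80% power for 7.1 points at SD 12 with 15 families per phase and alpha 0.05. The normal formula (1.96 + 0.84) × SD × √(2/n) gives 2.80 × 12 × 0.365 ≈ 12.3 points. The two-sided t calculation gives 12.72. Power for 7.1 points is about 35% (t), and 7.1 corresponds to about 45 per group. The stated figure does not reproduce, so 12.72 is the reference below. Sidedness is not stated; two-sided is assumed.

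**Power of the baseline comparison** (two-sided t, n = 15, df = 28). For a 0.5 SD imbalance the noncentrality is 0.5 × √(15/2) = 1.37, and power is 26% (about 34% at 20 per phase). A non-significant baseline test is weak reassurance.

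**Size of the possible bias.** The documents give neither the imbalance δ (in SDs of the covariate) nor the covariate-outcome correlation r. The ranges are assumptions: δ 0.2 to 0.5, r 0.2 to 0.5. Bias = δ × r × SD. Rejection with no true effect is the noncentral t probability with noncentrality δ × r × √(n/2).

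| δ | r | Bias at SD 12 | False-positive rate, n = 15 |
|---|---|---|---|
| 0.2 | 0.2 | 0.48 | 5.1% |
| 0.2 | 0.5 | 1.2 | 5.8% |
| 0.5 | 0.2 | 1.2 | 5.8% |
| 0.35 | 0.3 | 1.3 | 5.9% |
| 0.5 | 0.4 | 2.4 | 8.3% |
| 0.5 | 0.5 | 3.0 | 10.1% |

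As a share of the detectable difference, this is 0.48/12.72 = 4% to 3.0/12.72 = 24%. At SD 5 the bias is 0.2 to 1.25 points, and at SD 2 it is 0.08 to 0.5.

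**Chance imbalance.** If the cohorts differ only by chance, the unadjusted test keeps its 5% level over repetitions. The standard error of the baseline difference is √(2/15) = 0.365 SD, so a chance imbalance of at least 0.5 SD (0.5/0.365 = 1.37 standard errors) still arises in about 17% of studies this size.

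**What adjustment does.** In 20,000 simulated studies with δ = 0.5, r = 0.5 and 15 per phase, the unadjusted test rejects in 10.2%. With the covariate in the model, rejection is 5.3% and the bias is close to zero.

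**The case against.** The strongest reply is that the problem is potential rather than demonstrated. Both cohorts come from one clinic, under one set of inclusion criteria and one recruitment process, which limits differences in case mix. No document gives an imbalance or a correlation; most of the assumed range yields a false-positive rate below 6%, and only the corner near (0.5, 0.5) reaches 10%. The study is a pilot with no stated hypotheses. All of this stands, and it is why the point concerns the interpretability of an estimate more than error control.

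Some stronger readings are tempting but not supported:

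- A reader might infer that the protocol calls the 4a-versus-4b contrast an RCT. The label is attached to Cohort 2 (Aim 4b). It conflicts with the design, but it does not name that contrast.
- A reader might infer that the model excludes covariates. Section 14.1 is a short paragraph that names none; that is all the text shows.
- A reader might take the expected 40 enrolled of 100 screened (section 10.3) as evidence of selection. The figure can include ineligible families and is one ratio for both phases, so it says nothing about a difference between them.
- A reader might conclude that concussion history must be the covariate. Section 2.1 ties history and severity to the decision and to when retirement is raised, not to how well the decision is made. It treats being informed as part of a good decision and links poor information to lower socioeconomic status, and section 14.1 lists health literacy. The documents do not settle the choice.

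Timing also counts. The title-page note refers to a sample already recruited and smaller than planned, so an adjustment added now may not be prespecified.

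**Conclusion.** The point holds in limited form. The comparison is non-randomised, the description of Aim 4b as a pilot RCT does not fit it, and the primary analysis names no baseline covariate, either in section 14.1 or in the simplified plan. The contrast is therefore open to case-mix confounding. The documents do not show that it is biased, and they give no direction. The 0.5 to 3.0 points at SD 12 rest wholly on the assumed ranges, on a systematic shift in a single covariate, and on 15 families per phase; the final number may be smaller. Correcting the description is warranted whatever view is taken of the size. An adjusted estimate alongside the unadjusted one is a proportionate addition; replacing the primary model is more than the evidence supports.

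**What to change.** 1. Reconcile section 1.1 with section 5.1 by describing the Aim 4 comparison as non-randomised. State that covariate adjustment cannot remove calendar-period effects such as changes in season, provider or clinic practice.

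2. In section 14.1, report a covariate-adjusted estimate beside the unadjusted one, whatever the baseline comparison shows. Use one baseline covariate, at most two, from those already listed there (for example concussion history or health literacy). Choose it without reference to outcomes and justify the choice. Confirm that it is recorded before the aids are used: section 5.2 puts the aids before the appointment, while section 5.4 puts the first survey at the first visit, possibly in the waiting room.

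3. Apply the same to the simplified analysis if it replaces the SEM. Refer the condition effect to a t distribution with residual degrees of freedom or another stated small-sample correction: for observed scores at 15 per phase, maximum-likelihood Wald z tests reject 6.9% of the time under the null with no covariate and 7.4% with one. If outcomes have already been examined, label the adjusted estimate post hoc.

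**Cost.** This needs SAP wording and minor analysis work. Section 22.2.1 says that the number of past concussions may be collected on the survey platform, so that covariate probably needs no new data. Each covariate uses one degree of freedom per outcome equation. With one covariate that explains nothing, the variance rises by the factor 1 + 1/26 and df falls from 28 to 27, so the difference detectable with 80% power at SD 12 goes from 12.72 to 12.98 points. The covariate pays for itself once R² exceeds 0.040 (r about 0.20). The cost grows in a smaller sample: at 10 per phase the rise is from 15.90 to 16.45 with break-even R² 0.065, and at 8 per phase break-even is 0.088 (r about 0.30). These figures apply to observed scores, not latent outcomes.
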